2.7.2 Statistical hypothesis, model, and method of analysis

Methods of analyses for efficacy endpoints defined in [Section 2.7.1](#) are described below.

- The annualized rate of new or newly enlarged T2 lesions for Adult group will be estimated by a negative binomial regression model with log-link function, the total number of new or newly enlarged T2 lesions within 30 days from the last dose date (per subject) as the response variable. Natural log of time from screening scan in years will be used as the offset. The model will include baseline age and baseline volume of T2 lesions as continuous covariates. The estimated number of new or newly enlarged T2 lesions will be obtained together with the corresponding 95% confidence interval.

Supportive analyses: similar analyses may also be conducted to obtain the estimated annualized rate of new or newly enlarged T2 lesions at month 0 to month 12 and at month 12 to month 24 for Adult group.

Descriptive summary statistics (mean, median, standard deviation, min, max) for the number of new or newly enlarged T2 lesions will be provided by age group and by visit. Number and percentage of subjects free of new or newly enlarged T2 lesions will also be provided by age group.

- The number of Gd-enhancing T1 lesions per scan for Adult group will be estimated by a negative binomial regression model with log-link function, the total number of Gd-enhancing T1 lesions within 30 days from the last dose date (per subject) as the response variable. Natural log of the number of MRI scans will be used as the offset. The model will include baseline age and number of Gd-enhancing T1 lesions at baseline as continuous covariates. The estimated number of Gd-enhancing T1 lesions per scan will be obtained together with the corresponding 95% confidence interval.

Supportive analyses: descriptive summary statistics (mean, median, standard deviation, min, max) for the number of Gd-enhancing T1 lesions will be provided by age group and by visit. Number and percentage of subjects free of Gd-enhancing T1 lesions will also be provided by age group.

- Descriptive summary statistics (mean, median, standard deviation, min, max) will be provided by age group and by visit for the following: volume of T2 lesions, volume of Gd-enhancing T1 lesions, number of T1 hypo-intense lesions, volume of T1 hypo-intense lesions, change and % change in volume of T2 lesions, Gd-enhancing T1 lesions and T1 hypo-intense lesions from baseline.

2.7.3 Handling of missing values/censoring/discontinuations

As a general rule, missing data will not be imputed in any secondary endpoint analyses. For MRI parameters, only assessments taken within 30 days from the last dose date will be included in the analysis.

2.8 Safety analyses

All safety analyses will be conducted using the SAF. The safety cutoff is defined as 45 days (5 times the half-life of fingolimod, 9 days) after the last dose administration of study drug. Unless

explicitly otherwise stated, only data up to and including the safety cut-off will be included in the analysis and data beyond this time point for a given subject will be excluded from the safety analysis.

The assessment of safety will be primarily based on the frequency of adverse events (including death and non-fatal serious adverse events). Additional safety assessments include laboratory tests, vital sign measures, ECG evaluations, ophthalmic and dermatology. Clinically significant findings in these additional safety assessments and other will be reported as adverse events and analyzed as such.

2.8.1 Adverse events (AEs)

An adverse event (AE) is any untoward medical occurrence (i.e. any unfavorable and unintended sign [including abnormal laboratory findings], symptom or disease) in a clinical investigation subject after providing written informed consent for participation in the study. That means that a subject can report AEs before having started study medication. For reporting purposes, the main focus will be on treatment emergent adverse event (TEAE), defined as any AE which started on or after the day of first dose of study medication or events present prior to the start of treatment but increased in severity based on preferred term.

Except for serious TEAEs and deaths, only TEAEs up to and including the safety cut-off will be included in the analyses. All serious TEAEs and deaths will be included, regardless of the safety cut-off.

TEAEs will be reported by primary system organ class (SOC) and preferred term (PT) according to the most recent Medical Dictionary for Regulatory Activities (MedDRA). The MedDRA version used for reporting the study will be specified in a footnote of the tables, figures or listings (TFLs).

Overview of TEAE will be provided. The number and percentage of subjects reporting any TEAEs (referred to as incidence of any TEAEs in the following) will be summarized by age group, primary SOC and preferred term. Separate summaries will be provided for serious TEAEs, drug related TEAEs, TEAEs leading to permanent discontinuation of study treatment, TEAEs causing study treatment interruption, and most common TEAEs ($\geq 10\%$ in any of the age groups), which could be replaced by listings (for Child or even for both Adult and Child) if more appropriate. Additionally, the incidence of any TEAEs will also be summarized by age group, primary SOC, preferred term, and maximum severity (Mild, Moderate and Severe). Missing severity will not be imputed.

If a subject reported more than one AE within the same primary SOC, the subject will be counted only once with the maximum severity at the SOCs level, where applicable.

All AEs will be presented in listings.

2.8.1.1 Adverse events of special interest / grouping of AEs

Selected tables will be produced for Adverse Events of Special Interest (AESI) (i.e. risks), which will be defined in the electronic case retrieval sheet (eCRS) at the time of analysis implementation (i.e. study DBL). Specifically, incidence of TEAEs that fulfill the risk search terms as defined in eCRS will be summarized by age group, risk name and preferred term.

Similarly, separate summaries will be provided for serious TEAEs that fulfill the risk search terms as defined in the eCRS (could be replaced by listing for Child if more appropriate). Additionally, incidence of any TEAEs that fulfill the search terms as defined in the eCRS will also be summarized by age group, risk name, preferred term and maximum severity.

2.8.2 Deaths

Detailed listing for deaths will also be provided. All deaths as recorded in the final database (i.e. up to DBL) will be included.

2.8.3 Laboratory data

The summary of laboratory evaluations will be presented for two groups of laboratory tests: Hematology and Chemistry. On presenting summary statistics, laboratory data will be grouped and displayed in an alphabetical order within the Hematology and Chemistry groups and subgroups.

Descriptive summary statistics (mean, median, standard deviation, Min and Max) of the change from baseline in the laboratory result to each study visit-window by age group will be presented. Change from baseline will only be summarized for subjects with both baseline and post-baseline values and will be calculated as:

$$\text{change from baseline} = \text{post-baseline value} - \text{baseline value}$$

For continuous variables databased as <lower limit, these will be imputed as being half of the lower limit.

The number and percentage of subjects with notable laboratory abnormalities (as defined in [Table 2-8](#) below) at any time post baseline will be presented by age group (or listing for the Child group if more appropriate). Frequency (%) distribution of key hematological parameters (absolute lymphocytes, absolute neutrophils, leukocytes, and platelet count), with categories defined by either upper limit of normal (ULN), actual values, or a ratio of actual value, will be presented by age group (or listing for the Child group if more appropriate).

Table 2-8 Criteria for notable laboratory abnormalities

Notable Values		
Laboratory Variable	Standard Units	SI Units
Serum glutamic oxaloacetic transaminase (SGOT) (AST)	>82 U/L	>82 U/L
Serum glutamic pyruvic transaminase (SGPT) (ALT)	>90 U/L	>90 U/L
Total bilirubin	≥ 2.0 mg/dL	≥ 34.2 μmol/L
RENAL FUNCTION / METABOLIC VARIABLES		
Creatinine	≥2.0 mg/dL	≥176 umol/L
Total cholesterol	≥ 240 mg/dL	≥ 6.21 mmol/L
Triglycerides	≥ 300 mg/dL	≥ 3.39 mmol/L
HEMATOLOGY VARIABLES		
Hemoglobin	≤ 10.0 g/dL	≤ 100g/L
Platelets (Thrombocytes)	≤ 100 k/mm ³	≤ 100 x 10 ⁹ /L
	≥ 600 k/mm ³	≥ 600 x 10 ⁹ /L

Leukocytes (WBCs)	$\leq 2.0 \text{ k/mm}^3$	$\leq 2.0 \times 10^9/\text{L}$
	$\geq 15 \text{ k/mm}^3$	$\geq 15 \times 10^9/\text{L}$
HEMATOLOGY VARIABLES: DIFFERENTIAL		
Neutrophils (absolute)	$\leq 1,000/\text{mm}^3$	$\leq 1 \times 10^9/\text{L}$
	$\geq 12,000/\text{mm}^3$	$\geq 12 \times 10^9/\text{L}$
Lymphocytes (absolute)	$<200/\text{mm}^3$	$<0.2 \times 10^9/\text{L}$
	$\geq 8,000/\text{mm}^3$	$\geq 8 \times 10^9/\text{L}$
Red blood cells (RBCs)	$<3,300,000/\text{mm}^3$	$<3.3 \times 10^{12}/\text{L}$
	$>6,800,000/\text{mm}^3$	$>6.8 \times 10^{12}/\text{L}$

RBC and Triglycerides are not collected on the "Hematology - Local Lab Results" page.

Number of subjects with newly occurring liver enzymes abnormalities at any time post-baseline will be summarized. Newly occurring liver enzymes abnormalities are defined in the table below.

Table 2-9 Criteria for newly occurring liver enzymes abnormalities

Laboratory Variable (unit)	Criteria
SGOT (AST) (U/L)	$>\text{ULN}$ $\geq 2 \times \text{ULN}$ $\geq 3 \times \text{ULN}$ $\geq 5 \times \text{ULN}$ $\geq 10 \times \text{ULN}$ $\geq 20 \times \text{ULN}$
SGPT (ALT) (U/L)	$>\text{ULN}$ $\geq 2 \times \text{ULN}$ $\geq 3 \times \text{ULN}$ $\geq 5 \times \text{ULN}$ $\geq 10 \times \text{ULN}$ $\geq 20 \times \text{ULN}$
Bilirubin (total) (umol/L)	$>\text{ULN}$ $\geq 2 \times \text{ULN}$ $\geq 34.2 \text{ umol/L}$

ULN=upper limit of normal; normal range in the local laboratory of each site will be applied to subjects in that site.

The results are presented in cumulative form, i.e. the highest actual laboratory value/upper limit value was used. If the value is $\geq 20 \times \text{ULN}$, it is also included in the $\geq 10 \times \text{ULN}$ category and all the above categories.

For the patients who missed the visits, but took off-site laboratory evaluations due to COVID19 (lockdown, site issue, subject concern or other), the off-site laboratory data will be included to analyze. The sensitivity analysis will be conducted to assess laboratory data (WBC, neutrophils, lymphocytes, ALT, AST, total bilirubin and platelets), with the only change to exclude off-site laboratory data. For this sensitivity analysis, summary of patients with clinically notable laboratory abnormalities by age group and summary of patients meeting potentially clinically significant criteria based on laboratory data will be presented.

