8.1 Screening

It is permissible to re-screen a participant if s/he fails the initial screening; re-screening should only occur after a participant has failed screening and re-screening window time is at the discretion of the investigator. A new participant ID should be assigned to the re-screened participant.

As per Section 4.6, during a Public Health emergency, alternative methods of providing continuing care may be implemented by the investigator as the situation dictates. If allowable by a local Health Authority and depending on operational capabilities, phone calls, virtual contacts (e.g. tele consult) or visits by site staff/ home nursing staff to the participant's home, can replace on-site study visits, for the duration of the disruption until it is safe for the participant to visit the site again. In exceptional cases and after discussing with the study team, participant go to another hospital for safety test will be permitted.

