8.4.1 Laboratory evaluations

Laboratory samples will be collected as described in [Table 8-3](#) and analyzed by the local lab. Investigators will be asked to comment on these abnormalities on the respective lab result page, including a notation of the clinical significance of each abnormal finding in the participant's source documents. The laboratory sheets will be filed with the source documents. Mandatory hematology and chemistry test results should be recorded on the eCRF.

Any diagnosis (or signs or symptoms if a diagnosis is not possible) associated with the abnormal findings should be recorded on the adverse event eCRF.

Clinically notable laboratory findings are defined in Appendix 1.

In case of increases in liver function test (LFT), refer to Appendix 7 Guidance on Safety Monitoring.

In case of decreases in lymphocytes, refer to Guidance on monitoring of participants with notable lymphopenia in Appendix 7 Guidance on Safety Monitoring.

If the COVID-19 pandemic limits or prevents on-site study visits, the method of collection of samples may be modified by Novartis if applicable and if modified, will be communicated to the Investigator. In exceptional cases and after discussing with Novartis, safety tests could be performed outside of the investigator sites.

Table 8-3 Laboratory Evaluations

Test Category	Test Name
Hematology	Hemoglobin, Platelets, White blood cells (WBC), Differential (Basophils, Eosinophils, Lymphocytes, Monocytes, Neutrophils, Other)

Test Category	Test Name
Hepatitis B test	HBV surface antigen, surface antibody, E antigen, E antibody, core antibody; if abnormal finding on HBV surface antigen, HBV DNA copies test will be performed.
Coagulation Function	Prothrombin time
Chemistry	ALT , AST , Creatinine, Direct Bilirubin, Total Bilirubin, Total Cholesterol
Urinalysis	Macroscopic Panel /Dipstick (Color, Blood, Glucose)
Additional tests	HIV antibodies
Pregnancy Test	Serum / Urine pregnancy test

8.4.2 **Electrocardiogram (ECG)**

ECGs will be collected at Screening visit, Day1, Month 1, Month 3, Month 6, Month 12, Month 18, Month 24, Premature discontinue from treatment (EOT), premature discontinue from study (EOS), Follow-up visit according to the assessment schedule and as needed if study drug is restarted after interruption.

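### The Table 2-9 footnote ties the ULN to the participant's site, so off-site liver results run by another laboratory can be misgraded in the ULN-based rows

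*SAP*

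**What the plan says.** Protocol 8.4.1 has laboratory samples "analyzed by the local lab", so no central laboratory supplies a common reference range. For the ULN-based liver summary, the SAP 2.8.3 footnote to Table 2-9 sets the range by site: "normal range in the local laboratory of each site will be applied to subjects in that site". It names no exception. A further note says how the multiple is formed: "the highest actual laboratory value/upper limit value was used". Categories are cumulative and count participants at any time after baseline.

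For participants who missed visits because of COVID-19 but had tests elsewhere, SAP 2.8.3 states that "the off-site laboratory data will be included to analyze". Elsewhere can mean a different hospital. Protocol 8.1 says that, in exceptional cases, "participant go to another hospital for safety test will be permitted", and Protocol 8.4.1 says that "safety tests could be performed outside of the investigator sites".

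The SAP also plans a sensitivity analysis "with the only change to exclude off-site laboratory data". It covers seven analytes, including ALT, AST and total bilirubin, and has two outputs. One is the clinically notable abnormalities by age group. For the other, a "summary of patients meeting potentially clinically significant criteria based on laboratory data will be presented".

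Neither document says that an off-site laboratory's own reference range will be collected or used.

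**The concern.** A site-specific range is needed only because ranges can differ between laboratories. The same reasoning calls for hospital B's range on a result from hospital B. The footnote instead follows the participant: if site A's participant is tested at hospital B, the value comes from B and the ULN from A. The resulting multiple belongs to neither laboratory.

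At stake is the trial's ULN-based liver summary. Protocol 1.1 lists transaminase elevation among the safety areas of note for this drug. Because Table 2-9 uses the highest multiple at any time and cumulates downwards, a single off-site result can set a participant's category. The primary endpoint is not touched.

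**Working it through.** The documents state no figure that depends on this rule, so there is nothing to reproduce. The check is algebra, with assumed ULNs where the documents give none.

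**Inputs from the documents**
- Cut-offs for ALT and AST: above ULN, then 2, 3, 5, 10 and 20 x ULN. For bilirubin: above ULN, 2 x ULN, and a fixed 34.2 umol/L (SAP Table 2-9).
- Fixed limits: AST above 82 U/L, ALT above 90 U/L, bilirubin at least 34.2 umol/L (SAP Table 2-8).
- Background rates on fingolimod 0.5 mg: 8.0% at 3 x ULN or more and 1.8% at 5 x ULN or more (Protocol 1.1). Planned size: about 100 participants.

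**Assumed, for illustration only**
- ALT and AST ULN between 35 and 50 U/L; bilirubin ULN between 17.1 and 23 umol/L.

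**Step 1: relative error.** Multiple under the footnote = value / ULN(site). Multiple on the testing laboratory's range = value / ULN(off-site). Their ratio is ULN(off-site) / ULN(site). Over the assumed ALT/AST range this runs from 35/50 = 0.70 to 50/35 = 1.43, and is 1 when the ranges agree.

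**Step 2: which results change category.** At cut-off k, a result is graded differently only if it lies between k x the smaller ULN and k x the larger ULN.

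| Assumed ULNs | Cut-off | Results graded differently |
|---|---|---|
| 40 vs 50 U/L | 3 x | 120 to below 150 U/L |
| 35 vs 50 U/L (extreme) | 2 x | 70 to below 100 U/L |
| 35 vs 50 U/L | 3 x | 105 to below 150 U/L |
| 35 vs 50 U/L | 5 x | 175 to below 250 U/L |
| Bilirubin 17.1 vs 23 umol/L | 2 x | 34.2 to below 46 umol/L |

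**Step 3: direction.** Take an off-site ALT of 130 U/L.
- Site ULN 40, off-site ULN 50: graded 130/40 = 3.25; on the testing laboratory's range 130/50 = 2.60. The footnote overgrades.
- Site ULN 50, off-site ULN 40: graded 2.60; on the testing laboratory's range 3.25. The footnote undergrades.

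**Step 4: rows that cannot move.** Table 2-8 and the 34.2 umol/L row of Table 2-9 involve no ULN. Changes from baseline use raw values.

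**Step 5: how small the counts are.** 8.0% and 1.8% of 100 give about 8 and 2 participants. One reclassified participant would be about 1/8 of the first count and about half (1/1.8 = 0.56) of the second. This shows how sensitive the counts are; it does not predict that a reclassification will occur. The rates are for transaminases together, whereas Table 2-9 lists ALT and AST separately, so single rows may hold fewer cases.

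**The case against.** The strongest reply is that misgrading needs several conditions at once. The sample must be run by a different laboratory, that laboratory's ULN must differ, the result must fall between the two cut-offs, and no other result may already place the participant in that category. Off-site need not mean another laboratory: Protocol 8 and 8.1 allow home visits by site staff, and Protocol 8.4.1 allows the collection method to be modified, so the site laboratory may still run some samples. Another hospital is for exceptional cases. All of this stands. A reader might infer that every off-site liver value, or every liver summary, is wrong; the documents do not support that.

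A reader might also infer that the sensitivity analysis leaves Table 2-9 out, since its first output uses fixed limits. That is not established. The SAP does not define the criteria for the second output. The seven analytes listed are the four key haematological parameters of SAP 2.8.3 plus the three analytes of Table 2-9, which suggests that the second output may include the ULN-based summary. What can be said is that the text does not settle it. Even if Table 2-9 is included, dropping off-site results isolates their effect but does not grade them correctly in the main table.

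Finally, SAP 2.8 bases the safety assessment primarily on adverse events, clinically significant findings are reported as such, and Protocol 12 plans no hypothesis testing. This limits the consequence. It does not make the stated rule right.

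**Conclusion.** The point holds in conditional form. The footnote is a stated rule that, followed literally, pairs one laboratory's result with another's ULN for any off-site sample run elsewhere. The affected outputs are the ULN-based rows of Table 2-9 for ALT, AST and total bilirubin, and the error can go either way. Over the assumed ALT/AST ULNs of 35 to 50 U/L, the reported multiple is 0.70 to 1.43 times the multiple on the testing laboratory's own range. If the ranges agree, nothing changes.

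The number of participants affected is unknown, because the documents give neither the laboratories' ULNs nor the number of off-site samples. The consequence is confined to one descriptive safety summary. The change is still worth making, because that summary concerns a named risk of the drug, its expected counts are small, and the correction is cheap.

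**What to change.** Replace the range sentence in the Table 2-9 footnote with: *The reference range of the laboratory that analysed the sample is applied to each result; if the range of an off-site laboratory was not recorded, the site range is used and the result is flagged.*

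Results without a recorded range should stay in the table. Leaving them out would remove clear elevations from a safety summary: an ALT of 400 U/L is 400/50 = 8.0 to 400/35 = 11.4 x ULN anywhere in the assumed range.

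In the sensitivity analysis without off-site data, name the Table 2-9 summary as an output and define the criteria used for the second output.

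The cost is a short SAP edit and a small amount of work to carry the ULN from off-site reports into the dataset. The documents do not show whether the eCRF captures that range, so some site queries may be needed. No participant procedure changes.

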2.8.4 Other safety data

2.8.4.1 ECG and cardiac imaging data

ECG data will be collected at selected scheduled visits as specified in [\[Protocol Table 8-1\]](#). Clinically significant findings from ECG evaluations will be reported as AEs and included in the analysis of AEs. ECG parameters include mean heart rate, mean PR interval, mean uncorrected QT interval, mean QRS duration, and QT corrected using Fridericia's correction formula (all as collected on the ECG CRF). Descriptive statistics of each ECG parameter will be provided for each baseline and post-baseline visit-window by age group. Similar summaries will also be provided for change from baseline ECG parameters for each post-baseline visit-window. Criteria in corrected QT interval as defined in [Table 2-10](#) will be provided for each criterion by age group (or listing for the Child group if more appropriate).

Table 2-10 Abnormality criteria for corrected QT interval

	Male subjects	Female subjects
1	>450 msec	>470 msec
2	>500 msec	> 520 msec
3	30 - 60 msec increase from Baseline	
4	>60 msec increase from Baseline	

For first dose administration monitoring, ECG parameters and change from pre-dose in ECG parameters by timepoint during 1st and 2nd dose (if necessary) administration will be summarized by age group. The number and percentage of subjects meeting the criteria in corrected QT interval (at any timepoint post-dose during 1st and 2nd dose (if necessary) administration) will be presented by age group (or listing for the Child group if more appropriate).

For non by-visit summaries, visits defined by visit-windows will not be used. All available data from scheduled and unscheduled visits will be considered.

For the patients who missed the visits, but took off-site ECG evaluations due to COVID19 (lockdown, site issue, subject concern or other), the off-site ECG data will be included to analyze. The sensitivity analysis will be conducted to assess ECG data, with the only change to exclude off-site ECG data. For this sensitivity analysis, number and percentage of patients meeting the criteria in corrected QT interval and the corrected QT interval criteria (at any timepoint post-dose during first/second dose administration) by age group will be presented.

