Initiation of fingolimod treatment results in a transient decrease in heart rate and infrequently induces atrio-ventricular (AV) block. In MS clinical trials, the mean maximal decrease in heart rate after the first dose intake was 12~ 13 bpm and was seen at ~6 hours post-dose. Heart rates below 40 beats per minute were rarely observed in patients on fingolimod 0.5 mg/day. Heart rate progressively returned to baseline within 1 month of dose initiation despite continued dosing. In addition, a mild increase in blood pressure of approximately 2 mmHg diastolic and 3 mmHg systolic on average. This onset after approximately 1 months of treatment initiation persisted with continued treatment but reversed upon cessation of therapy. Hypertension was reported as an adverse event in 6.5% of patients on fingolimod 0.5 mg/day and in 3.3 % of patients on placebo in the 2-years placebo controlled study.

Liver enzyme elevations were seen in clinical trials. Asymptomatic elevations in serum levels of hepatic transaminases ≥ 3 x upper limit of normal (ULN) and ≥ 5 x ULN, were observed in 8.0% and 1.8% of patients treated with fingolimod 0.5 mg/day respectively compared to 1.9% and 0.9% for patients receiving placebo. The majority of elevations occurred within 12 months of therapy and returned to normal, generally within 2 months of discontinuation of therapy.

Macular edema occurred in 0.5% of patients treated with fingolimod 0.5 mg/day. Approximately 75% of cases occurred within the first 3-4 months of therapy. The macular edema generally improved or resolved spontaneously after drug discontinuation. The risk of developing macular edema appears to be increased in MS patients with a history of uveitis. There is limited data on fingolimod in MS patients with diabetes mellitus. In earlier renal

transplant clinical studies where patients with diabetes mellitus were included, therapy with fingolimod 2.5 mg/day and 5 mg/day resulted in a 2-fold increase in the incidence of macular edema. MS patients with diabetes mellitus are therefore expected to be at a higher risk for macular edema.

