At Day1, two to three ECGs will be performed. The first ECG will be performed on Day 1 to check the I/E criteria again. If the participant is eligible to be enrolled, the ECG result will be recorded as pre-dose ECG. The second ECG will be performed approximately 6-hours post-first-dose. If extended monitoring is needed, then a third ECG will be performed by the end of extended monitoring.

If study drug treatment is interrupted and treatment re-initiation meets the requirement for observation, the above procedures will be repeated, identical to procedures conducted at Day 1.

For any ECGs with participant safety concerns, an additional ECG must be performed to confirm the safety finding. Clinically significant abnormalities must be recorded on the CRF as adverse events.

All the below ECG parameters will be captured in the eCRF: heart rate, PR interval, QRS duration, QT and QTc interval. Any diagnoses (or signs or symptoms if a diagnosis is not possible) associated with the abnormal findings should be recorded on the adverse event eCRF.

8.4.3 **Pregnancy and assessments of fertility**

To confirm an eligibility of a woman of child bearing potential for the study, a blood pregnancy test should be performed at Screening visit. Participants, who are determined and documented to be surgically-sterile or post-menopausal for 12 months or longer prior to Screening, are not required to undergo pregnancy testing.

Women of child-bearing potential, defined as all women physiologically capable of becoming pregnant, including women whose career, lifestyle, or sexual orientation precludes intercourse with a male partner and women whose partners have been sterilized by vasectomy or other means, unless they meet the following definition of post-menopausal: 12 months of natural

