12.5.1 Safety endpoints

For all safety analyses, the safety set will be used.

Safety assessments will include: adverse events (AEs), laboratory tests, vital signs, ophthalmic examinations, dermatology assessment, and ECG data.

An AE will be considered as treatment-emergent adverse event (TEAE) if it starts on or after first treatment with fingolimod during the study. TEAE will be summarized by presenting the number and percentage of participants experiencing adverse events by system organ class (SOC), preferred term (PT) and severity of adverse events.

Severe AEs, serious AEs, drug related AEs and the AEs leading to premature discontinuation of study drug will be presented in a similar format as adverse events.

Laboratory and vital sign data will be presented by clinical notable ranges.

The clinical notable abnormality of ophthalmic and dermatology data will be summarized as AE.

The (uncorrected) QT interval of ECG will be corrected according to the Bazett's and Fridericia formulae and then summarized by visit. Abnormal findings from ECG will be summarized as AE as well.

For the first dose administration monitoring, the change from pre-dose of pulse rate and BP at each hour will be summarized and the individual plots over time will be provided. The incidence rate of abnormal ECG findings at pre-dose and 6 hours post-dose, as well as the corrected QT change in category from pre-dose to 6 hours post-dose will be presented.

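### The SAP uses a site-entered QTc as Fridericia, although the protocol names no formula for that field and planned to derive the correction, so one formula is not assured across sites and time points

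*SAP*

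**What the plan says.** Three places describe the corrected QT, and they do not match.

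- **Protocol 12.5.1 (Safety endpoints)** makes the correction an analysis step with two formulae: "The (uncorrected) QT interval of ECG will be corrected according to the Bazett's and Fridericia formulae and then summarized by visit". For first-dose monitoring it adds that "the corrected QT change in category from pre-dose to 6 hours post-dose will be presented".
- **Protocol 8.4.2 (Electrocardiogram)** lists what sites enter: "All the below ECG parameters will be captured in the eCRF: heart rate, PR interval, QRS duration, QT and QTc interval". There is one QTc field, and no formula is named. Exclusion criterion 4 also uses QTc without a formula.
- **SAP 2.8.4.1 (ECG and cardiac imaging data)** gives the last ECG parameter as "QT corrected using Fridericia's correction formula (all as collected on the ECG CRF"). No derivation follows, and Bazett does not appear in the visible SAP text.

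SAP Table 2-10 then classifies corrected QT in two ways. Criteria 1 and 2 are absolute limits (above 450 and 500 msec for males, above 470 and 520 msec for females). Criteria 3 and 4 are changes: "30 - 60 msec increase from Baseline", and a rise of more than 60 msec. SAP 2.8.4.1 and 2.8.5.4 apply the table during first-dose monitoring and, where needed, second-dose monitoring.

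**The concern.** The protocol planned to compute the correction centrally from QT. The SAP relies on a number entered by the site, and the protocol never asks for that number to be a Fridericia value. About 10 to 15 centres take part, and no central ECG reading is described. Off-site ECGs taken because of COVID-19 enter the main analysis. The planned sensitivity analysis removes off-site ECGs, but it does not address differences in formula between sites or between a participant's ECGs.

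The choice of formula matters most at the first dose. Protocol 1.1 reports that "the mean maximal decrease in heart rate after the first dose intake was 12~ 13 bpm", seen at about 6 hours, and protocol 8.4.2 says "The second ECG will be performed approximately 6-hours post-first-dose". The change from pre-dose is therefore measured when heart rate is expected to be lowest. Bazett and Fridericia respond differently to a change in rate, so a difference in formula can pass for a change in QTc. ECG is a listed secondary safety endpoint, and this is the setting in which the plan looks at QTc change most closely.

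**Working it through.** The plan gives no figure to reproduce here. The check is how far apart the two formulae would put the same ECG.

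**Inputs from the documents:** heart-rate fall 12 to 13 bpm; post-dose ECG at about 6 hours; change classes 30–60 and >60 msec.

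**Assumptions, not in the documents:** pre-dose heart rate (HR) 60 to 90 bpm; pre-dose Fridericia QTc 380 to 450 msec.

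**Formulae:** with RR = 60/HR in seconds, QTcB = QT/RR^(1/2) and QTcF = QT/RR^(1/3). Dividing one by the other gives QTcB = QTcF × (HR/60)^(1/6).

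**Example: QTcF 420 msec pre-dose, HR 75 falling to 62 bpm.** The factors are (75/60)^(1/6) = 1.0379 and (62/60)^(1/6) = 1.0055. Pre-dose QTcB is 420 × 1.0379 = 435.9 msec.

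| True QTcF change | Post-dose QTcB | Change read with Bazett both times |
|---|---|---|
| 0 | 420 × 1.0055 = 422.3 | −13.6 msec |
| +30 | 450 × 1.0055 = 452.5 | +16.6 msec |
| +60 | 480 × 1.0055 = 482.6 | +46.7 msec |

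**Over the full assumed ranges, Bazett both times:**

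| True QTcF change | Change read | Understated by |
|---|---|---|
| 0 | −17.9 to −9.6 msec | 9.6 to 17.9 msec |
| +30 | +10.9 to +21.8 msec | 8.2 to 19.1 msec |
| +60 | +39.7 to +53.1 msec | 6.9 to 20.3 msec |

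A true rise of exactly 30 msec misses criterion 3 everywhere in this range.

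**How wide the affected bands are.** Write F0 and F1 for the pre-dose and post-dose factors (HR/60)^(1/6). The true rise that reads as c msec is (c + QTcF × F0)/F1 − QTcF. In the example this is 43.4 msec for c = 30 and 73.2 msec for c = 60. Over the full ranges it is about 38 to 50 msec for c = 30 and about 67 to 81 msec for c = 60. True rises between each cut-off and these values go one class too low. Larger rises are still classed correctly, unless they pass the next cut-off.

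**Absolute criteria.** A QTcF of 450 msec reads as a QTcB of 437 at 50 bpm, 444 at 55, 450 at 60, 452 at 62, 462 at 70 and 467 at 75. Below 60 bpm Bazett reads low and under-flags. Above 60 bpm it reads high and over-flags.

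**Different formulae at the two time points (same example, no true change).** Bazett then Fridericia gives 420 − 435.9 = −15.9 msec. Fridericia then Bazett gives 422.3 − 420 = +2.3 msec. The error depends on which ECG carries which formula.

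**The case against.** The strongest objection is that the harm depends on a document that is not available. The only statement about the formula behind the collected value is in the SAP, which calls it Fridericia. The protocol's bare QTc does not contradict that, and the eCRF field may be labelled Fridericia. The SAP authors also checked CRF content elsewhere: 2.8.3 notes two laboratory tests that are not collected. A reader might infer from the mismatch that sites enter Bazett values and that the analysis will hide first-dose QT prolongation. The documents do not support that, for four reasons.

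- No passage records a Bazett entry.
- The understatement concerns criteria 3 and 4 only. Above 60 bpm the absolute criteria would err the other way.
- The affected bands are limited. A rise just over 60 msec would move down a class but would still be flagged.
- Other views of the data remain. Uncorrected QT and heart rate are summarised with their change from pre-dose, clinically significant ECG findings are recorded as adverse events, and the 6-hour ECG is compared with the pre-dose ECG before discharge.

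A reader might also infer that Bazett was dropped without explanation. SAP Section 4, on changes to protocol-specified analyses, is blacked out, so this cannot be said.

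All of this stands, and it makes the consequence conditional. It does not remove the gap. Even a field labelled Fridericia would hold a site-entered number, and the SAP does not check it against QT and heart rate, although the protocol specified the calculation. Nor does the study's descriptive aim, without hypothesis tests, make the class counts less dependent on a uniform definition.

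**Conclusion.** The point holds as a gap in specification with a conditional consequence. The documents do not ensure that the QTc in Table 2-10 follows one formula at all sites and time points, and the visible SAP text departs from the protocol's planned derivation.

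If entered values were Bazett both before and after the first dose, a heart-rate fall of 12 to 13 bpm would understate the QTc change by about 7 to 20 msec: 10 to 18 with no true change, and 7 to 20 at a true rise of 60 msec. Mixed formulae within a participant would distort the change by an amount that depends on the order.

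The size rests on the assumed pre-dose heart rate and QTc ranges and on the mean heart-rate fall applying to the participant. Whether any of it occurs rests on the eCRF, which is not among the documents. No primary estimate or decision rule depends on this table. The case for the change is that it costs almost nothing and settles the question whatever the field contains.

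**What to change.** In SAP 2.8.4.1, replace the reliance on the collected value with a derivation: QTcF = QT/(60/HR)^(1/3), from the recorded uncorrected QT and heart rate of the same ECG. Apply it to every ECG, including first-, second- and restart-dose monitoring. Use it for Table 2-10 and all change-from-baseline and change-from-pre-dose summaries, and name the formula in the table. Keep the site-entered QTc for listings only.

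Reconcile the Bazett summary with protocol 12.5.1, either by giving it alongside or by stating that it is dropped, unless the blacked-out Section 4 already does so.

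The cost is one programmed derivation in the ECG dataset, a second if Bazett is kept, and a short text change. QT and heart rate are already on the eCRF, so there is no new data collection and no added work for sites.
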